7.9.3.4 Determination of Patients/Data for Analysis

The Enrolled Population and, at each FU visit, the subset of subjects that were indicated for an ICD/CRT-D will be included in the analysis as described in Section 7.9.3.3.

7.9.4 Secondary objective 3: Incidence of CV Mortality

Characterize the proportion of post-acute MI patients who experience cardiovascular mortality.

7.9.4.1 Hypothesis

There are no hypotheses for this objective, as this is a characterization objective.

7.9.4.2 Endpoint definitions

The endpoint will be defined as cardiovascular mortality.

7.9.4.3 Analysis methods

At each follow-up visit, the cumulative proportion of subjects who experienced cardiovascular mortality between each visit will be computed. A SAS code similar to the example SAS code shown in Section 7.9.1.3 will be used and the results will be shown in a table similar to Table 7 below.

Table 7: Proportion of post-acute MI patients who experienced cardiovascular mortality

Region	3 months visit	6 months visit	12 months visit
China	XX/XX (XX.XX%)	XX/XX (XX.XX%)	XX/XX (XX.XX%)
Taiwan	XX/XX (XX.XX%)	XX/XX (XX.XX%)	XX/XX (XX.XX%)
India	XX/XX (XX.XX%)	XX/XX (XX.XX%)	XX/XX (XX.XX%)
Korea	XX/XX (XX.XX%)	XX/XX (XX.XX%)	XX/XX (XX.XX%)
South East Asia	XX/XX (XX.XX%)	XX/XX (XX.XX%)	XX/XX (XX.XX%)
Middle East, Africa, Central Asia and Turkey	XX/XX (XX.XX%)	XX/XX (XX.XX%)	XX/XX (XX.XX%)
Overall	XX/XX (XX.XX%)	XX/XX (XX.XX%)	XX/XX (XX.XX%)

Further, for subjects who experience cardiovascular mortality, a subject's time to death will be computed in months from enrollment to date of death. If a subject does not meet the endpoint, the subject will be censored at the later of their last follow-up visit or exit. A competing risks event curve will be generated with accompanying 95% confidence bounds and non-cardiovascular mortality accounted for. A SAS code similar to the example code below will be used.

```
proc lifetest data=KM plots=cif(test) timelist=0 1 2 3 4 5 6 7 8 9 10 11 12;
  by region;
  time T*Status(0) /eventcode=1;
run;
```

where T will be the time in months from enrollment to date of cardiovascular death and Status will be an indicator variable with 3 values: 0 for censored observations, 1 for patients who died for cardiovascular death and 2 for subjects who died for non-cardiovascular death. Results will be determined separately for each region and overall.

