9.7. Study Exit

At 3-month follow-up, if a subject has an LVEF $\geq 50\%$, the subject will be exited from the study. Subject who remain in the study after 3-month follow-up should remain in the study until the 12-month follow-up is completed or until all data required to meet study objectives have been collected (whichever comes first). Either an in-office visit or phone call is required for study exit.

A study exit eCRF is required for all subjects. Prior to exiting a subject from the study, it is recommended to follow the subject until all AEs are resolved. Following exit, subjects will continue to receive standard medical care. Upon exiting from the study, no further study data will be collected or study visits will occur for the subject. Exited subjects will not be replaced with newly enrolled subjects.

Subjects are urged to remain in the study as long as possible, but may be exited from the study for any of the following situations:

- Study closure
- Subject lost to follow-up (refer to Section 9.11.1)
- Subject did not meet inclusion/exclusion criteria
- Subject did not provide consent or data use protection authorization
- Subject chooses to withdraw (refer to section 9.11.2 for more information)
- Investigator deems withdrawal necessary (e.g. medically justified, inclusion/exclusion criteria not met)
- Subject exited study at the 3 months visit if the 3-month LVEF is $\geq 50\%$
- Subject completed study after 12 months visit
- Subject Death

For study exit visits the following information is required:

- Reason for exit
- Final interrogation file (or CareLink transmission) for subjects implanted with Medtronic device
- Cardiovascular Adverse events, Study Deviations and System Modification

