9.11. Subject Withdrawal or Discontinuation

9.11.1. Lost to Follow-Up

In the case that the subject is determined to be lost to follow-up, a minimum of two attempts to contact the subject must be documented. The recommended method of contact is one letter and one phone record or two letters. In addition, follow the regulations set forth by the governing IRB/EC.

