12.3.4.3. Analysis methods

At each follow-up visit, the cumulative proportion of subjects who experienced cardiovascular mortality between each visit will be computed.

Further, for subjects who experience cardiovascular mortality, a subject's time to death will be computed in months from enrollment to date of death. If a subject does not meet the endpoint, the subject will be censored at the later of their last follow-up visit or exit. A competing risks event curve will be generated with accompanying 95% confidence bounds and non-cardiovascular mortality accounted for.

Results will be determined separately for each relevant geography/country.

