12.5. Missing data

Missing data will not be imputed. For survival endpoints, subjects who do not meet the endpoint and exit or die prior to completing follow-up will be censored at the date of death or exit for endpoints that do not include the type of death the subject experienced (e.g. cardiovascular death).

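### Censoring at the exit date counts unobserved time as event-free for subjects lost to follow-up, and lowers the cardiovascular-death curve to the extent that deaths in that gap go undiscovered

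*SAP*

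**What the plan says.** SAP 7.9.4.3 plans a competing-risks curve for cardiovascular death, timed in months from enrollment, with non-cardiovascular death as the competing event. For a subject without the event, "the subject will be censored at the later of their last follow-up visit or exit". Protocol 12.3.4.3 carries the same sentence. Protocol 12.5 extends exit-date censoring to survival endpoints generally: anyone who leaves or dies early without the event "will be censored at the date of death or exit". That sentence applies where the death in question is not itself part of the outcome.

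SAP 7.9.3.3 plans competing-risks curves for meeting the referral criteria, referral, stratification visit, indication and implant. It gives a code for censored observations but no censoring date, so Protocol 12.5 is the only rule available there.

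Protocol 9.7 lists loss to follow-up among the exit reasons. On paperwork it states "A study exit eCRF is required for all subjects"; as to contact, the same section says "Either an in-office visit or phone call is required for study exit". For a lost subject, Protocol 9.11.1 requires that "a minimum of two attempts to contact the subject must be documented". Neither document defines the exit date of a subject who cannot be reached, limits how late loss may be declared, uses a last-known-alive date, or requires a vital-status check.

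**The concern.** Protocol 9.7 allows no visits or data after exit, so the later of the two dates is in practice the exit date. That is right for a subject who exits at a visit or call, because status is known that day. An unreachable subject cannot have that contact. If the exit is dated when the site gives up, the time since last contact was observed by nobody, yet the subject sits in the risk set as a survivor. Deaths in that time can enter the numerator only if someone discovers them.

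What is at stake is the level of the 12-month cardiovascular-death curve in each region and overall. The curve is the one cardiovascular-mortality analysis in the plan that can allow for loss, because Protocol 12.5 rules out imputation and SAP 7.4 makes no allowance for missing data in the main analyses.

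**Working it through.** **Inputs.** The documents give no cardiovascular mortality, no separate loss rate and no lag from last contact to exit, so there is no plan figure to reproduce. The only attrition figure (SAP 6.1) is 10% for drop-out and mortality combined, to the 3-month visit. Mortality, loss, lag and discovery below are therefore assumptions, shown as ranges.

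**How long the gap could be.** In Protocol 9.6, Table 3, the 6-month window closes at day 210 and the 12-month window at day 395. A subject last seen at day 90 is not overdue until day 210 (210 - 90 = 120 days). One last seen at day 180 is not overdue until day 395 (395 - 180 = 215 days). Sites may declare loss sooner, but nothing obliges them to.

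**Formula.** Take a constant hazard λ, a share L lost with last contact at month u, exit g months later, and a share f of the deaths in the gap discovered. During the gap the estimated hazard is about λ[1 - L(1 - f)]. The relative bias at month T is therefore about -L(1 - f)g/T.

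**Single-cause calculation, f = 0.** Last contact is at u = 2.5 months from enrollment (the 3-month visit, if enrollment is about two weeks after the MI). The curve is read at T = 11.8, so that an exit at 11.9 is still in the risk set. A 12-month risk of 10% gives a true value of 1 - 0.90^(11.8/12) = 9.84%; a risk of 6% gives 5.90%.

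| Lost | Exit (month) | g within T | -Lg/T | Curve, true 9.84% | Curve, true 5.90% |
|---|---|---|---|---|---|
| 10% | 6.5 | 4.0 | -3.4% | 9.52% | 5.71% |
| 20% | 6.5 | 4.0 | -6.8% | 9.20% | 5.51% |
| 10% | 11.9 | 9.3 | -7.9% | 9.07% | 5.44% |
| 20% | 11.9 | 9.3 | -15.8% | 8.31% | 4.98% |

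The relative bias runs from about -3% to about -16%. Censoring at last contact returns the true value here, because no later death is found.

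**With competing non-cardiovascular death (2% assumed), f = 0.** At a true 12-month incidence of 6% and 10% lost:
- loss spread evenly, lag 1 month: 5.95% (-0.05 points);
- loss spread evenly, lag 3 months: 5.87% (-0.13 points);
- last contact month 3, exit month 12: 5.55% (-0.45 points).

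Over 54 combinations (mortality 3, 6, 10%; loss 5, 10, 20%; six loss and lag patterns) this component was always downward. With lags of 1-3 months it was -0.01 to -0.48 points. The extreme was -2.0 points (-20% relative): 10% mortality, 20% lost from enrollment and exit at month 12.

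**Against sampling error.** 1.96√(p(1 - p)/200) gives 2.4, 3.3 and 4.2 points at p = 3, 6 and 10%. With 1,200 pooled it gives 1.0, 1.3 and 1.7 points.

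**If later deaths are found.** Single-cause model, true 9.84%, 10% lost:

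| f | Exit (month) | Exit-date rule | Last-contact rule |
|---|---|---|---|
| 0.5 | 6.5 | 9.68% | 10.01% |
| 0.5 | 11.9 | 9.46% | 10.23% |
| 1 | 6.5 | 9.84% | 10.19% |
| 1 | 11.9 | 9.84% | 10.62% |

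With 20% lost, f = 0.5 and exit at 11.9, the exit-date rule gives 9.07% and last-contact censoring 10.72%.

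**The case against.** The best defence is that the gap is an inference. The exit form is not among the documents, and if sites enter the last-contact date as the exit date there is no bias. That stands as a limit on size. It does not rescue the rule, because nothing requires that practice.

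Second, deaths must be reported, Protocol 11.3.1 has sites seek information on deaths at remote locations, and lost subjects are pursued by letter or phone. Some deaths after last contact will be found. If all are, the exit-date rule is exact and last-contact censoring is too high, because it keeps the found deaths and drops the survivors early. With about half found, the two rules err by similar amounts in opposite directions. This stands, and it is why the fix needs a sensitivity analysis.

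Third, the reach is modest: a descriptive curve for a secondary objective without a hypothesis. Table 7 reports simple proportions that use no censoring date.

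A reader might infer more than this supports:
- That the curve as a whole is biased downward. Subjects with LVEF ≥50% leave at 3 months; if they are at lower risk, their removal pushes the later curve up. The net direction is not established.
- That regions with more loss will look better. This depends on filing delay and death discovery by region, which the documents do not give.
- That phone visits make late loss likely. They could equally reduce it.

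**Conclusion.** The point holds in limited form. As written, the rule can count unobserved time as survival for subjects lost to follow-up, and no provision elsewhere prevents it. Subjects who exit with contact, LVEF ≥50% exits at the 3-month visit and 12-month completers are not affected.

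The -3% to -16% range requires 10-20% lost at month 2.5, exit four or more months later and no later death found. Its top end needs 20% lost, exit near month 12 and no discovery, so it is not an expected value. With lags of 1-3 months the effect is well inside per-region sampling error. With heavy loss and late exits it becomes material, more so in the pooled curve, where sampling error is smaller and the bias is not. The case for changing the rule is that its error depends on an undefined administrative date, and that the correction is cheap.

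**What to change.** In SAP 7.9.4.3 and Protocol 12.3.4.3 and 12.5, replace the censoring rule with: subjects lost to follow-up, or exited without a contact at exit, are censored at the last date known alive (last visit, call or dated record); subjects exited with a visit or call are censored at the exit date.

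In SAP 7.9.3.3, add a rule where none exists: meeting the referral criteria, referral, stratification visit, indication and implant are censored at the last date on which that status was assessed. Being known alive does not establish referral or implant status.

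Report exit-date censoring as a sensitivity analysis, with the number of lost subjects, the interval from last contact to exit, and the number of deaths discovered after last contact, by region. The reader can then see which rule is likely to err, and by how much.

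The cost is a wording change and one derived date, from visit and contact dates that sites already record. The downside is slightly less recorded follow-up, slightly wider bounds, and some upward bias if many late deaths are found: small at modest loss, larger if loss is heavy and gaps are long, as the 10.72% case shows.

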11.3.2. Death Classification and Reporting

Sufficient information will be required in order to properly classify the subject's death. The Investigator shall classify each subject death per the following definitions:

- **Sudden Cardiac Death (SCD):** Natural death due to cardiac causes, indicated by abrupt loss of consciousness within one hour of the onset of acute symptoms; preexisting heart disease may have been known to be present, but the time and mode of death are unexpected. If the time of onset cannot be determined, SCD will alternatively be defined as any unexpected cardiac death occurring out of the hospital or in the emergency room as dead on arrival.
- **Non-sudden Cardiac Death:** All cardiac deaths that are not classified as sudden deaths, including all cardiac deaths of hospitalized subjects on inotropic support.
- **Non-cardiac Death:** A death not classified as a cardiac death.
- **Unknown Classification:** Unknown death classification is intended for use only when there is insufficient or inadequate information to classify the death.

Table 7 Subject Death Classification Responsibilities

What is classified?	Who classifies?	Classification Parameters
Death Classification	Investigator	Sudden Cardiac, Non-sudden Cardiac, Non-cardiac, Unknown

Regulatory reporting of subject deaths will be completed according to local regulatory requirements.

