7.9.1.3 Analysis Methods

Subjects will be evaluated during their three months visit (chronic phase, $\geq 40-90$ days after MI) for determination of the need for SCD risk stratification and management. As of this visit, subjects will be partitioned into several groups: died of cardiovascular causes prior to reaching the 3 months visit, exited or died of non-cardiovascular or unknown causes prior to reaching 3 months visit, reached the 3 months visit and exited because of $\text{LVEF} \geq 50\%$, reached the 3 months visit and had at least one reason for referral for SCD risk stratification and management, reached the 3 months visit and had no reason for referral for SCD risk stratification and management.

Subjects classified as “died of cardiovascular causes” will be all subjects with subject status “death” within the exit CRF and with primary cause of death “non-sudden cardiac death” or “sudden cardiac death” within the death CRF.

Subjects classified as “exited or died of non-cardiovascular or unknown causes” will be all subjects with subject status “death” within the exit CRF and with primary cause of death “non-cardiovascular death” or “unknown classification” within the death CRF and all subjects with subject status “adverse event, lost to follow-up, physician decision, sponsor request or withdrawal by subject” in the exit CRF.

Subjects classified as “reached the 3 months visit and exited because of $\text{LVEF} > 50\%$ ” will be all subjects that will have completed the three months visit and will have subject status “other” within the exit CRF and will have a result of LVEF measurement higher or equal than 50% within the LVEF CRF.

Subjects classified as “reached the 3 months visit and had at least one reason for referral” will be all subjects that will have completed the three months visit and that in the referral CRF will have answer “yes” to the question “does the subject meet referral criteria” and will have at least one reason for referral selected underneath the question “if yes, indicate referral criteria met”.

Subjects classified as “reached the 3 months visit and had no reason for referral” will be all subjects that will have completed the three months visit and that will have answer “no” to the question “does the subject meet referral criteria” in the referral CRF.

Descriptive statistics will be used to summarize these groups and displayed as shown in the example Table 2 below.

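### SAP 7.9.4.3 has no status code for deaths of unknown cause and, read literally, censors them; the cardiovascular-mortality results also carry no bound for such deaths

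*SAP*

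**What the plan says.** **Classes collected.** Protocol 11.3.2 gives the investigator four classes: "Sudden Cardiac, Non-sudden Cardiac, Non-cardiac, Unknown". The last is a restricted but genuine category: "Unknown death classification is intended for use only when there is insufficient or inadequate information to classify the death".

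**CV-mortality analysis.** SAP 7.9.4.3 sets the status variable to "0 for censored observations, 1 for patients who died for cardiovascular death and 2 for subjects who died for non-cardiovascular death". Unknown cause is not mentioned in that section. The section also states: "If a subject does not meet the endpoint, the subject will be censored at the later of their last follow-up visit or exit". For SAP Table 7, "the cumulative proportion of subjects who experienced cardiovascular mortality between each visit will be computed"; the analysis set is the Enrolled Population (SAP 7.9.4.4).

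**Protocol rule on missing data.** For survival endpoints, Protocol 12.5 says that subjects who do not meet the endpoint and who exit or die early "will be censored at the date of death or exit for endpoints that do not include the type of death the subject experienced".

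**Where unknown cause is assigned.** SAP 7.9.1.3 identifies CV death as sudden or non-sudden cardiac death on the death form. It places unknown cause in the group "exited or died of non-cardiovascular or unknown causes". That grouping serves the disposition summaries at 3 months, repeated at 6 and 12 months. SAP 7.9.4.3 does not refer to it.

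**Methods promised.** Protocol 12.3.1.3, 12.3.2.3 and 12.3.4.3 call for competing-risk analyses with mortality (for CV death, non-CV mortality) accounted for. The pathway curves in SAP 7.9.3.3 give code 2 to any subject who died.

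**The concern.** An unknown-cause death does not meet the CV-mortality endpoint as the SAP identifies it, and it is not a recorded non-CV death either. It therefore falls to the default, which is censoring. Censoring assumes that the subject could still die of CV causes later, which a dead subject cannot. It is also at odds with the competing-risk method that the same section prescribes.

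A second matter is larger. In SAP Table 7 an unknown-cause death stays in the denominator and cannot enter the numerator. In the curve it is not a CV event under code 0 or code 2. Neither output tells the reader how many such deaths there were or how much they could matter. Results are presented by region. If the completeness of death records differs between regions, CV-mortality figures could differ for that reason alone, and the reader could not tell.

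**Working it through.** **1. The plan's own figures.** The documents state no CV-mortality rate and no unknown-cause rate, so there is no planned figure to reproduce here. The only planning figure used is the regional size, as a scale: 54 / 0.30 = 180, and 180 / 0.90 = 200 (SAP 6.1).

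**2. What the text does with an unknown-cause death.**

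| Place | Treatment |
|---|---|
| SAP 7.9.4.3, status values | none given |
| SAP 7.9.4.3, censoring sentence | censored at the later of last visit or exit |
| Protocol 12.5 | censored at date of death or exit |
| SAP 7.9.1.3, disposition groups | pooled with non-CV deaths and exits |
| SAP 7.9.3.3, pathway curves | code 2, as for any death |

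Taken alone, the censoring sentence would also censor non-CV deaths. Status 2 overrides it for them; nothing overrides it for unknown cause.

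**3. Effect of the code. All rates are assumptions.** Take 12-month probabilities of 6% CV, 2% non-CV and u = 1%, 2% or 4% unknown death. In 200 subjects that is 12, 4, and 2, 4 or 8 deaths. Assume constant cause-specific hazards and no early exits.

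- Unknown as competing event (code 2): cumulative incidence = 6.00%.
- Unknown as CV (code 1): cumulative incidence = 6% + u.
- Unknown censored (code 0): the hazards of the two remaining causes are 8/(8 + u) of the total (u in percent), and CV is 6/8 of those two. So cumulative incidence = 0.75 × [1 − (0.92 − u)^(8/(8+u))], with u as a fraction in the base and in percent in the exponent.
  - u = 1%: 0.75 × (1 − 0.91^(8/9)) = 0.75 × 0.0804 = 6.03%
  - u = 2%: 0.75 × (1 − 0.90^(8/10)) = 0.75 × 0.0808 = 6.06%
  - u = 4%: 0.75 × (1 − 0.88^(8/12)) = 0.75 × 0.0817 = 6.13%

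| Unknown deaths per 200 | Code 0 | Code 2 | Code 1 | SAP Table 7, non-event / CV |
|---|---|---|---|---|
| 2 | 6.03% | 6.00% | 7.0% | 6.0% / 7.0% |
| 4 | 6.06% | 6.00% | 8.0% | 6.0% / 8.0% |
| 8 | 6.13% | 6.00% | 10.0% | 6.0% / 10.0% |

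An Aalen-Johansen calculation on 200 subjects with these counts gives the same values.

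**4. Higher assumed rates.** In simulations with 10% CV, 2% non-CV and 5% unknown death, half of the deaths falling in the first 3 months, code 0 against code 2 gives 10.24% against 9.98% with no early exits. With 30% exiting at 3 months it gives 10.47% against 10.20%. The rise is 0.26 to 0.27 points. Counting unknown as CV gives 14.88% and 15.12%, about 5 points above code 2.

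**5. Reading.** Censoring moves the estimate slightly upward, by 0.03 to 0.13 points in step 3. Whether unknown deaths are CV moves it by roughly the full unknown proportion, 1 to 4 points in step 3.

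**The case against.** The strongest reply is that the SAP does classify these deaths. SAP 7.9.1.3 is the only place that assigns them to a group, it puts them with non-CV deaths, and a programmer would carry that over as Status 2. The censoring sentence is loosely drafted and cannot be meant literally, since it would also censor non-CV deaths. In addition, code 0 against code 2 is trivial beside sampling error: the Wilson 95% interval for 12/200 is about 3.5 to 10.2%. The objective is secondary and descriptive, with no hypothesis.

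Most of this stands. It shows that Status 2 is probably intended and that the coding alone changes little. It does not supply the missing instruction, which is then left to be settled when the data are programmed. It also does not answer the absence of a bound.

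Four stronger readings are tempting, and the documents do not support them:

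- A reader might infer that censoring makes reported CV mortality 14 to 40% too low. Those ratios (1/7 and 4/10) compare the known-CV figure with one in which every unknown death is CV. They are an upper bound on assumed rates and do not come from censoring, which pushes the estimate slightly up.
- A reader might infer that the device-implant curve is biased in the same way. SAP 7.9.3.3 already codes every death as 2, so that would happen only if Protocol 12.5 were followed over the SAP.
- A reader might infer that unknown-cause deaths will be common because later visits may be by phone. Protocol 11.3.1 requires cause and description of death, asks for records where available, and makes the site responsible for attempting to retrieve information on remote deaths. Protocol 11.3.2 classes an unexpected out-of-hospital cardiac death as sudden even when onset time cannot be determined. The frequency cannot be predicted from the documents.
- A reader might infer that these deaths vanish from the report. Deaths are recorded as fatal adverse events and individual events are listed (SAP 8), and SAP Table 2 includes them, pooled with other exits. What is missing is a separate count and its effect on CV mortality.

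**Conclusion.** The point holds as a gap in specification with a cheap remedy. SAP 7.9.4.3 does not code unknown-cause deaths, and two written defaults would censor them, against SAP 7.9.1.3 and the protocol's competing-risk methods. The bias from that alone is about 0.03 to 0.13 points at assumed rates of 6% CV, 2% non-CV and 1 to 4% unknown, and about 0.26 to 0.27 points at the higher assumed rates.

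The larger issue is the missing bound. Unknown-cause deaths could add up to their whole proportion to CV mortality, and the planned outputs would not show it. That maximum is reached only if every such death was CV. Every size given here rests on assumed rates. Counting these deaths as non-CV in the main SAP Table 7 is acceptable if the bound stands beside it.

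**What to change.** 1. In SAP 7.9.4.3, code deaths of unknown cause as Status 2 at the date of death, citing the grouping in 7.9.1.3. Limit the censoring sentence to subjects not known to have died.
2. Repeat the CV-mortality curve and SAP Table 7 with unknown-cause deaths coded as CV death, labelled as an upper-bound sensitivity analysis. The main analysis is then the matching lower bound.
3. Report the number of unknown-cause deaths by region and overall.
4. Reword Protocol 12.5 so that a subject who exits alive without the endpoint is censored at exit, and any death that is not the endpoint is a competing event at its date. Simply deleting the reference to death would leave the clause about type of death attached to subjects who only exited. The new wording would match Status 2 in SAP 7.9.3.3 and 7.9.4.3.

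The cost is wording plus one extra curve and table, from data already collected. Under Protocol 12.1 an amendment is needed only when a principal feature changes, so item 4 can wait for the next amendment, with the reason given in the study report meanwhile.

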Table 2: Number (%) of subject in each group between enrollment and the 3 months visit

		Enrolled Population
Region 1	Died of cardiovascular causes	XX/XX (XX.XX%)
	Exited or died of non-cardiovascular or unknown causes	XX/XX (XX.XX%)
	Reached the 3 months visit and exited because of LVEF \geq 50%	XX/XX (XX.XX%)
	Reached the 3 months visit and had reasons for referral	XX/XX (XX.XX%)
	Reached the 3 months visit and had no reasons for referral	XX/XX (XX.XX%)
Region 2	Died of cardiovascular causes	XX/XX (XX.XX%)
	Exited or died of non-cardiovascular or unknown causes	XX/XX (XX.XX%)
	Reached the 3 months visit and exited because of LVEF \geq 50%	XX/XX (XX.XX%)
	Reached the 3 months visit and had reasons for referral	XX/XX (XX.XX%)
	Reached the 3 months visit and had no reasons for referral	XX/XX (XX.XX%)
...
Overall	Died of cardiovascular causes	XX/XX (XX.XX%)
	Exited or died of non-cardiovascular or unknown causes	XX/XX (XX.XX%)
	Reached the 3 months visit and exited because of LVEF \geq 50%	XX/XX (XX.XX%)
	Reached the 3 months visit and had reasons for referral	XX/XX (XX.XX%)
	Reached the 3 months visit and had no reasons for referral	XX/XX (XX.XX%)

The same summary statistics will be computed at the 6 months and at the 12 months visits and displayed in tables similar to Table 1, except for the group “exited because of LVEF \geq 50%” as patients are exited from the study for this reason at the 3 months visit only.

Note that at the three months visit, subjects with a LVEF \geq 50% will be exited from the study regardless of other reasons for referral. The proportion of those subjects that had a reason for referral other than LVEF will be computed by region and overall.

Among the subjects with a reason for referral during their three months visit, the proportions and Wilson score 95% CI of those who were referred for sudden cardiac death risk (SCD) stratification and management will be computed.

The subjects with a reason for referral (denominator) will be all subjects that at the three months visit will have at least one referral criterion met in the referral CRF. The subjects referred (numerator) will be

all subjects that will have completed the three months visit and that will have answer “yes” to the question “has the subject been referred or invited for SCD risk stratification” in the referral CRF.

An example SAS code for the computation of the proportions for each region is provided below:

```
proc freq data = referral;
  by region;

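### SAP reports cardiovascular mortality, but its only death-category mapping counts cardiac deaths alone and SAP 7.9.4 names no categories (low severity)

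*SAP*

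**What the plan says.** **Endpoint.** SAP 7.9.4.2 states only: "The endpoint will be defined as cardiovascular mortality". Protocol 12.3.4.2 is no fuller. SAP Table 7 is titled "Proportion of post-acute MI patients who experienced cardiovascular mortality". The Status variable for the cumulative incidence curve in SAP 7.9.4.3 is 0 for censored, then "1 for patients who died for cardiovascular death and 2 for subjects who died for non-cardiovascular death". No form field or value is named, and there is no code for a death of unknown cause.

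**Mapping.** The only rule that turns form values into a cardiovascular death is in SAP 7.9.1.3: "Subjects classified as “died of cardiovascular causes” will be all subjects with subject status “death” within the exit CRF", with primary cause "non-sudden cardiac death” or “sudden cardiac death” within the death CRF". Deaths recorded as "non-cardiovascular death” or “unknown classification” within the death CRF" are pooled with study exits. The result is the SAP Table 2 row "Died of cardiovascular causes". The summary is then repeated: "The same summary statistics will be computed at the 6 months and at the 12 months visits".

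**Source classification.** Protocol 11.3.2 and Protocol Table 7 give the investigator, and nobody else, four classes: sudden cardiac, non-sudden cardiac, non-cardiac and unknown. Non-cardiac is every death not classed as cardiac. Protocol Table 4, which defines cardiovascular adverse events, covers the heart, blood vessels and circulation, and lists stroke and peripheral vascular disease. Protocol 11.3.1 has each death entered on both an adverse event form and a death form.

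**The concern.** Cardiac mortality is narrower than cardiovascular mortality; the difference is vascular death, with fatal stroke as the obvious case. The plan names the wider quantity as a secondary objective, collects deaths in classes that cannot separate it out, and writes down one mapping, which yields the narrower quantity. A reader who compares the result with cardiovascular mortality from another source may be comparing different things.

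The stake is the meaning of a reported figure, by region and overall. The endpoint is descriptive with no hypothesis, so no test or sample size depends on it. There is also an internal consistency risk. SAP Table 2 (repeated at 6 and 12 months) and SAP Table 7 both report cardiovascular deaths at 3, 6 and 12 months. If 7.9.4 were programmed with a different rule, two tables with the same label could disagree.

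**Working it through.** The plan gives no expected mortality or cause split, so there is no stated figure to reproduce. The check is first of text, then an illustration.

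**Step 1: follow one fatal stroke through the documents.**

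| Place | Result |
|---|---|
| Adverse event form, Protocol Table 4 | cardiovascular event |
| Death form, Protocol 11.3.2 classes | non-cardiac |
| Death form, value names used in SAP 7.9.1.3 | no value fits: neither cardiac value, nor *non-cardiovascular* if stroke is cardiovascular |
| SAP Table 2 | outside the cardiovascular row unless coded as cardiac |
| SAP Table 7 and the curve | not stated; Status 2 if the Protocol classes and the 7.9.1.3 mapping are used |

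The third line matters. The form itself is not in the documents, and the two documents name its remaining value differently. With the Protocol's wording, vascular deaths are lost to the competing event. With the SAP's wording, the investigator must choose: *non-cardiovascular* or *unknown* loses the death, while *non-sudden cardiac* counts it.

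**Step 2: illustrative size.** All inputs are assumed: 12-month all-cause mortality 8% (range 6–10%); shares of deaths 65% cardiac, 10% unknown, *v* vascular and 25% − *v* other, with *v* = 0, 5 or 10%. With constant hazards, cumulative incidence is all-cause mortality × share.

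- Cardiac only: 8% × 0.65 = 5.20%.
- Cardiac plus vascular: 8% × (0.65 + *v*) = 5.20%, 5.60%, 6.00%.
- Shortfall: 0, 0.4 and 0.8 points.
- Share of cardiovascular deaths left out: *v*/(0.65 + *v*) = 0, 7.1% and 13.3%, whatever the all-cause rate.
- At 6% mortality: 3.90% against 3.90–4.50%. At 10%: 6.50% against 6.50–7.50%.

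**Step 3: expected counts.** Further assumptions: 30% of subjects exit at month 3 (LVEF of 50% or more) and drop-out is 10% over 12 months. Monthly hazards are −ln(0.92)/12 = 0.00695 for death and −ln(0.90)/12 = 0.00878 for drop-out, sum 0.01573; deaths are 0.4418 of all departures.

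- Months 0–3: 0.4418 × (1 − e^(−0.0472)) = 0.0204.
- Still followed after month 3: 0.9539 × 0.70 = 0.6677.
- Months 3–12: 0.6677 × 0.4418 × (1 − e^(−0.1416)) = 0.0389.
- Total 0.0593, or 11.86 deaths per 200 and 71.2 per 1,200.

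At *v* = 5% that is 0.6 vascular deaths in a region of 200 and 3.6 in 1,200. The crude overall figure is 0.0593 × 0.65 = 3.85%, against 0.0593 × 0.70 = 4.15%. Wilson 95% intervals are 2.0–7.7% for 8/200 and 2.9–5.1% for 46/1,200, so the difference lies well inside sampling error.

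**Step 4: unknown cause and censoring.** Counting the assumed 10% of unknown-cause deaths as cardiovascular as well gives 8% × 0.80 = 6.40% at *v* = 5%, against 5.60% without them. That uncoded choice moves the figure more than the vascular deaths do.

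SAP 7.9.4.3 also censors any subject who does not meet the endpoint at the later of last visit or exit. Read literally, this includes a non-cardiovascular death, which the same section codes as Status 2. Protocol 12.5 likewise censors at the date of death when the death is not of the endpoint's type. Censoring such deaths would give 1 − 0.92^0.65 = 5.28% instead of 5.20%. The difference is small, but the text contradicts itself.

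**The case against.** The case against is strong on several points.

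- *SAP 7.9.4 does not adopt the 7.9.1.3 mapping.* This stands: it cites that section only for example code. A reader might infer that SAP Table 7 and the curve will certainly be cardiac mortality, but the documents support that only conditionally. The SAP Table 2 row is not conditional, because its rule is written out.
- *The error is not shown to go one way.* This stands. A reader might infer that the figure can only be too low, by exactly the number of vascular deaths. That needs the Protocol's class names on the form. If the SAP's *non-cardiovascular* is on the form, vascular deaths may be partly or wholly counted, and a figure relabelled as cardiac could even be too high.
- *Protocol Table 4 defines adverse events, not deaths.* This is correct, and an event form and a death form may use different schemes. Table 4 is used here only as the documents' sole statement of what cardiovascular covers.
- *The mapping is explicit, so a reader of the SAP can see what is counted.* True for SAP Table 2. It does not help a reader of the results, or anyone looking for the rule in 7.9.4.
- *The effect is trivial.* Under the assumptions it is small and may be zero. That limits the severity; it does not remove the need to define a named secondary endpoint.

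**Conclusion.** The point holds at low severity. The cardiovascular-death row of SAP Table 2, at each visit, counts cardiac deaths under a cardiovascular label. SAP Table 7 and the curve would do the same if the mapping carries over, and otherwise they have no stated definition. If the Protocol's classes are applied, vascular deaths become the competing event and the figure is too low. Because the Protocol and SAP name the remaining class differently, direction and size cannot be settled from the documents.

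The illustrated shortfall of 0–0.8 percentage points rests wholly on the assumed 8% mortality and cause shares. It is probably small and may be zero. It would be wrong to infer any effect on the primary endpoint, the sample size or a hypothesis test.

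**What to change.** 1. Reconcile the death-category names between Protocol 11.3.2 and SAP 7.9.1.3, checking both against the death form.
2. In SAP 7.9.4.2, list the death-form values assigned to Status 1 and Status 2, including unknown cause. SAP 7.9.1.3 already groups unknown with non-cardiovascular; if 7.9.4 follows it, say so.
3. Then choose one of two routes.
   - *Relabel.* Call SAP Table 7, the curve and the SAP Table 2 row cardiac mortality, and explain in the study report how this differs from the name of the protocol objective. The cost is wording only; the downside is a measure narrower than that objective.
   - *Keep the cardiovascular label.* Add vascular deaths identified from the recorded cause of death and the MedDRA term, with the investigator's class shown alongside, since Protocol Table 7 makes the investigator the sole classifier. Under the assumptions above, this means reviewing about 0.25 × 71.2 = 18 non-cardiac deaths in 1,200 subjects (13–22 over 6–10% mortality). The data are already collected. The downside is some uncertainty in assigning deaths from text, because hospital records and certificates arrive only if available.
4. Reconcile the censoring sentence in SAP 7.9.4.3 and the rule in Protocol 12.5 with Status 2 for non-cardiovascular deaths.
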